5.1. Subject Disposition

Subject disposition will be summarized/listed for the randomized population by:

- Number and percentage of subjects who withdraw prior to receive randomized study medication
- Number and percentage of subjects who completed the study
- Number and percentage of subjects who withdrew from the study; further summarized by the reason for withdrawal from the study.

5.2. Subject Eligibility

Subject eligibility, such as inclusion and exclusion criteria will be presented in listings.

5.3. Demographic and Baseline Characteristics

Demographic and baseline characteristics will be listed and summarized descriptively for all subjects by treatment group for the safety population. Demographic and baseline characteristics include, but are not limited to: age, gender, ethnicity, race, body weight, height, body mass index (BMI), Liver fat via MRI-PDFF, Visceral fat via MRI, HbA1c, C-peptide, insulin, fasting plasma glucose, total cholesterol, HDL, LDL, VLDL, and triglycerides. The denominator of the percentage of subjects will be the number of subjects in the safety population at each cohort/dose level (placebo subjects will be pooled into one treatment group).

5.4. Medical History

Medical history will be coded using Medical Dictionary for Regulatory Activities (MedDRA, version 22.0) and summarized/listed by system organ class (SOC) and preferred term (PT) by cohort/dose level (placebo subjects will be pooled into one treatment group) for the safety population.

5.5. Study Drug Administration

Study drug administration data will be listed.

5.6. Extent of Exposure

Exposure will be summarized for the safety population. The summary of exposure will include the number of doses received, total dose administered, and the duration of exposure by cohort/dose level. Duration of exposure will be defined as the last dose date of treatment minus the first dose date of treatment.

Total duration of exposure to study drug (weeks) = (last dose date – first dose date +7)/7

5.7. Prior Medications and Concomitant Medications

Concomitant medication refers to medications that were administered after administration of the IP (includes the medication that start before IP and continue to be used together). Prior medication is defined as any medication that start and end before administration of the IP.

The WHO Drug Dictionary Enhanced (B3 WHO Drug Global version 2019 March) will be used to categorize the verbatim descriptions of medications into the ATC classification system. Each verbatim name will be classified by anatomical main group (ATC level 1), therapeutic subgroup (ATC level 2), pharmacological subgroup (ATC level 3), chemical subgroup (ATC level 4), and trade name in the database.

The number and percentage of subjects receiving concomitant medications will be summarized by cohort/dose level, and by anatomical therapeutic chemistry (ATC) classification, ATC level 2 and level 4, for the safety population. Prior medications will only be listed.

5.8. Protocol Deviations

Protocol deviations will be listed. Category of the protocol deviations will be included in the listing.

6. Statistical Methods of Analysis

6.1. General Considerations

Summary and analysis of Part 1 and Part 2 will be separate. Placebo subjects within each part of the study will be pooled in summaries and listings. Exploratory analysis for subgroup of subjects being impacted by COVID-19, versus those not being impacted, may be conducted to assess missing data due to COVID-19. As the number of subjects in the subgroup analysis will be much smaller than the original planned population, caution should be taken when interpreting the inferential statistical results. Please refer to Sections 6.3 and 6.4 for COVID-19 subgroup analyses.

All data collected in the EDC and external data sets will be listed using the safety population.

6.1.1. Statistical Notation and Presentation

The continuous variables will be summarized by number of observations (n), mean, standard deviation (SD), median, minimum (min), and maximum (max). For categorical variables, frequency and percentage in each category will be provided. For log-normal distributed data, geometric mean, standard error (SE) of the geometric mean, and coefficient of variation (CV) will also be provided. The geometric mean is calculated as the exponential of the arithmetic mean calculated from data on a log scale. The geometric CV is calculated as $CV\% = 100\% * \sqrt{(\exp(\sigma^2) - 1)}$, where σ is the standard deviation of the data on the natural log scale.

Means, least squares (LS) means, and medians will be rounded to 1 decimal place greater than the precision of the original value. SDs, SEs, and confidence intervals (CIs) will be rounded to 2

decimal places greater than the precision of the original value. Minimum and maximum values will be rounded to the precision of the original value. Percentages for summarizing categorical data will be rounded to one decimal place. P-values will be presented with 4 decimal places and values less than 0.0001 will be presented as <.0001.

All inferential statistical testing will be two-sided and conducted at the 0.05 significance level, unless specified otherwise. No multiplicity adjustment will be used for this study.

6.1.2. Study Baseline

Baseline will be defined as the last non-missing observation obtained prior to the administration of the first dose of study medication, unless otherwise specified.

The mean value of the 3 baseline ECG measurements collected at Day -2 will serve as each subject's baseline for all post-dose comparisons.

6.1.3. Handling of Multiple Observations or Out of Window Observations

Per COVID-19, additional modifications were made to the visit schedule in protocol version 5.0; refer to Table 2 for schedule of events. It was noted that after the protocol amendment, the study might have 2 subjects from Cohort 4 and all subjects from Part 2 that follow the modified visit schedule.

For PK and PD data, if a blood sample was collected outside the protocol specified blood sampling time window, such data will still be included in data analysis, and the actual clock time will be used for PK and PD parameters calculations such as area under the curve. For PD data with multiple observations on the same day and time point, the last observation will be used.

All values, scheduled or unscheduled, will be presented in data listings.

On scheduled visits with missing assessments, unscheduled assessments within the visit window, if available, may be used for analysis. Assessments collected during scheduled visits that are outside the visit window can be used for analysis. A footnote will be added to tables where unscheduled visits are used to impute missing scheduled visits. For vital signs data, if measurements are duplicated within the visit window, the data from the unscheduled visit will be used and the average of the scheduled and unscheduled visits will be taken for summary table. A footnote will be added to table to highlight the exception.

6.1.4. Handling of Missing or Partial Dates

In cases of incomplete dates for adverse events or non-study medications, the missing component(s) will be assumed as the most conservative value(s) possible. The imputation rules are designed to conservatively capture adverse events as treatment-emergent and medications as concomitant. For example, the following algorithm for missing start date of adverse events will be followed:

- If “day” is the only missing field, impute the “day” as the later one between the first day of the month and the dosing date if their “month” are the same.
- If “day” and “month” are the only missing fields, impute the “day” and “month” as the later one between January 1 of the year or the dosing date if the “year” is the same as the dose date.
- If “day”, “month”, and “year” are all missing, to be conservative, the event will be assumed to occur on the same day as the dosing was administered.

Adverse events and medications with missing or partial end dates will be imputed to conservatively capture treatment-emergent or concomitant status.

Date imputation will only be used for computational purposes; e.g., identifying treatment-emergent adverse events or identifying concomitant medications. Actual data values, as they appear in the clinical database, will be shown in the data listings.

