6.2. Safety Analysis

6.2.1. Adverse Events

Adverse events (AEs) will be coded using MedDRA, version 22.0.

HM-GCG-102 Statistical Analysis Plan

AEs will be summarized for the safety population. AEs with onset on or after the date of informed consent but before the date of dosing of study medication will be considered pre-treatment AEs. All of AEs will be listed.

AEs with onset date/time on or after receiving the dosing of study medication, or pre-existing AEs that increase either severity or frequency on or after receiving the dosing of study medication will be considered as TEAE.

An overall summary of TEAEs will be generated.

TEAEs will be summarized by:

- SOC and PT
- SOC, PT, and maximum severity by treatment group
- TEAEs that are related to study medication per investigator's decision
- TEAEs leading to study discontinuation
- TEAEs that are serious (treatment-emergent SAEs)
- Adverse events of special interest:
 - Necrolytic migratory erythema
 - Cholelithiasis

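### The SAP's start-date imputation for AEs does not check the recorded end date, so an AE that ended before the first dose can be counted as treatment-emergent

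*SAP*

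**What the plan says.** SAP 6.1.4 states the aim first: "The imputation rules are designed to conservatively capture adverse events as treatment-emergent and medications as concomitant". It then gives three rules for an incomplete AE start date.

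- Only the day missing: the day is imputed "as the later one between the first day of the month and the dosing date if their" months agree.
- Day and month missing: they are imputed "as the later one between January 1 of the year or the dosing date if the" year agrees.
- Everything missing: "the event will be assumed to occur on the same day as the dosing was administered".

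End dates appear once: "Adverse events and medications with missing or partial end dates will be imputed to conservatively capture treatment-emergent or concomitant status". That sentence covers end dates that are themselves incomplete. It does not use a known end date to limit an imputed start. The section also restricts how imputed dates are used: "Date imputation will only be used for computational purposes; e.g., identifying treatment-emergent adverse events". Listings show the values as recorded.

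SAP 6.2.1 classes as pre-treatment those "AEs with onset on or after the date of informed consent but before the date of dosing of study medication". It classes as treatment-emergent an AE whose onset is at or after dosing, or a pre-existing AE that becomes more severe or more frequent after dosing. Neither definition mentions the end date.

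Protocol 10.4.2 defines a TEAE as a clinically significant event that was absent before exposure, or one already present that worsens after exposure. Protocol 10.4.3 has AEs recorded from signing of consent, with both start and end dates.

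**The concern.** Leaning towards treatment-emergent status is sound when the timing of an event is in doubt. When the end date is recorded and precedes the first dose, there is no doubt left: whatever the true start, the event was over before exposure. Applied as written, the rules can still place its start on the dosing day. The event then has a start later than its end and enters the TEAE tables.

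AE incidence is the first-listed primary safety endpoint (Protocol 10.3.1, SAP 3.1.1), and the groups are small. The situation can arise. Screening may take place up to 35 days before dosing (Protocol 10.1), AEs are collected throughout that period, and clinically significant laboratory abnormalities found from consent onward are recorded as AEs (Protocol 10.2.2).

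**Working it through.** The plan states no figure to reproduce here. The check applies the rules literally to test dates and then scales the effect of one error.

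**1. The rules on a test case.** Assumed dates: first dose 20 July 2020, recorded AE end 10 July 2020.

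| Start date as recorded | Start under SAP 6.1.4 | Status under SAP 6.2.1 | With an end-date check |
|---|---|---|---|
| July 2020, day missing | later of 1 July and 20 July = 20 July | TEAE | pre-treatment |
| 2020, day and month missing | later of 1 January and 20 July = 20 July | TEAE | pre-treatment |
| all parts missing | 20 July | TEAE | pre-treatment |
| June 2020, day missing | rule does not apply (month differs) | not moved to dosing | not affected |

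In the first three rows the imputed start is 20 − 10 = 10 days after the recorded end. Under Protocol 10.4.2 the event is not a TEAE: it was present before exposure and, being over, could not worsen afterwards.

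**2. How far each rule reaches.** Assumptions: onset spread evenly over Days −35 to −1, and dosing equally likely on any day of 2020. That gives 366 × 35 = 12,810 pairs of dosing day and onset day.

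- Onset in the dosing month: a month of L days contributes L(L − 1)/2 pairs. Seven months of 31 days, four of 30 and one of 29 give 7 × 465 + 4 × 435 + 406 = 5,401, and 5,401/12,810 = 42%.
- Onset in the dosing year: 35 + 34 + … + 1 = 630 pairs fall in the previous year, so (12,810 − 630)/12,810 = 95%.
- All parts missing: 100%, because the rule has no condition.

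These are shares of pre-dose onset days that each rule would capture if the start date were incomplete in that way. They say nothing about how often start dates are incomplete.

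**3. Effect of one misclassified subject on a preferred-term incidence.** The shift is at most 100/n percentage points. Planned sizes are from Protocol 5.1; placebo is pooled within each part (SAP 6.1).

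- Active group in Cohorts 1–3 and 5–7, n = 9: 100/9 = 11.1.
- Part 1 pooled placebo, n = 3 + 3 + 3 = 9: 11.1.
- Cohort 4 active, n = 15: 100/15 = 6.7.
- Part 2 pooled placebo, n = 15 + 3 + 3 + 3 = 24 if all cohorts run in full: 100/24 = 4.2.

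Cohort 4 may stop short and Cohorts 6 and 7 are optional, so the last two groups may be smaller and the shift correspondingly larger. Without Cohorts 6 and 7, for example, pooled placebo is 15 + 3 = 18 and the shift is 100/18 = 5.6.

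**The case against.** The best defence is that 6.1.4 asks for the most conservative value that is possible and introduces its rules as an example. A start after the recorded end is not possible, so a careful programmer would not produce one. The protocol's TEAE definition points the same way. This shows what was probably intended, but it does not supply the check: the section presents its rules as the algorithm to follow, and none of them refers to the end date.

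Other parts of the defence stand.

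- A reader might infer that all three rules always move the start to the dosing date. Only the third does; the first needs a matching month and the second a matching year.
- A reader might take 11.1 points as the expected distortion. It is a ceiling for groups of 9, reached only if the subject has no genuine TEAE of the same preferred term. Nothing in the documents shows that any such event exists.
- A reader might infer a bias against the active drug. Pre-dose events cannot be caused by treatment, the rules are the same in both arms, and SAP 6.2.1 specifies no test. No systematic difference between arms is shown.
- A reader might extend the point to medications. SAP 5.7 already defines a prior medication as one that starts and ends before the IP, so a recorded pre-dose end settles the matter.
- The error would be traceable, because listings keep the recorded dates.

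**Conclusion.** The point holds as a minor defect. As written, SAP 6.1.4 and 6.2.1 together can class an AE recorded as ended before the first dose as treatment-emergent, which contradicts Protocol 10.4.2. It needs an incomplete start date, an end date known to precede the first dose and, for two of the three rules, a month or year match. The number of such AEs is unknown, probably small and possibly zero. The size per affected subject is bounded as shown above, on the assumption of planned group sizes.

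One related wording point: 6.1.4 refers to the dosing date, although there are 12 weekly doses (Protocol 8.3). The first dose is the natural reading and is assumed here, but the section does not say so.

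**What to change.** Add to SAP 6.1.4: *If the known complete or partial end date shows that the AE ended before the first dose, the imputed start date is set no later than the end date and the AE is classified as pre-treatment.* In the same section, replace the dosing date with the first dose date.

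For medications, apply the SAP 5.7 definition: a recorded end before the first dose makes the medication prior.

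The cost is one sentence, one wording change and one line of code, made before the Part 2 lock. Part 1 was already locked when this SAP amendment was written (SAP Section 1). For Part 1, a query for AEs whose imputed start is later than the recorded end is enough, with any correction documented in the CSR.

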6.1.5. Handling Outliers and Unquantifiable Measurements

The following rules will be applied when PK blood samples are assayed as below the limit of quantitation (BLQ) or if individual concentration results are deemed implausible prior to database lock:

- For individual PK concentration plots: BLQ values will not be displayed but will be flagged for reference in the by-subject listings.

For the calculation of descriptive statistics of concentrations or derivation of PK parameters: values that are BLQ and values deemed implausible will be set to missing.

For safety laboratory abnormality assessments, and potentially some PD variables:

- Values that are recorded with “>” (greater than) or “<” (lower than) the normal ranges, except some categorical variables, the numeric values will be used for descriptive statistical summary. For example, a value of >900 mg/dL will be set to 900 mg/dL for descriptive summary, and will be printed as “>900 mg/dL” on by-subject listing.
- Range result of “Low” will be assigned if the value is less than the lower limit of the normal range.
- Range result of “High” will be assigned if the value is greater than the upper limit of normal.

6.2. Safety Analysis

6.2.1. Adverse Events

Adverse events (AEs) will be coded using MedDRA, version 22.0.

HM-GCG-102 Statistical Analysis Plan

AEs will be summarized for the safety population. AEs with onset on or after the date of informed consent but before the date of dosing of study medication will be considered pre-treatment AEs. All of AEs will be listed.

AEs with onset date/time on or after receiving the dosing of study medication, or pre-existing AEs that increase either severity or frequency on or after receiving the dosing of study medication will be considered as TEAE.

An overall summary of TEAEs will be generated.

TEAEs will be summarized by:

- SOC and PT
- SOC, PT, and maximum severity by treatment group
- TEAEs that are related to study medication per investigator's decision
- TEAEs leading to study discontinuation
- TEAEs that are serious (treatment-emergent SAEs)
- Adverse events of special interest:
 - Necrolytic migratory erythema
 - Cholelithiasis

6.2.2. Local Tolerability

The number and percentage of subjects with any injection site reactions will be summarized by treatment group over the entire study and by visit and time point. The number and percentage of subjects with specific site reactions such as pain on palpation, itching, erythema, edema, and induration will be summarized by visit, time point, and Draize scale. In addition, diameter of affected areas will be summarized descriptively by visit and time point.

6.2.3. Clinical Laboratory Assessments

All hematology, clinical chemistry, and urinalysis results (including serum amylase, serum lipase, coagulation, thyroid stimulating hormone (TSH), serum calcitonin, eGFR) will be summarized. eGFR will be calculated using the following formula:

$$175 \times (\text{creatinine in mg/dL})^{-1.154} \times (\text{age})^{-0.203} \times (0.742 \text{ if female}) \times (1.212 \text{ if black})$$

$$175 \times (\text{creatinine in } \mu\text{mol/L divided by } 88.42)^{-1.154} \times (\text{age})^{-0.203} \times (0.742 \text{ if female}) \times (1.212 \text{ if black})$$

Laboratory assessments that are outside of normal ranges and/or with potential clinical importance will be summarized and flagged in the listings. Shift tables of hematology, clinical chemistry, and urinalysis results will be generated to summarize the normal and abnormal (with clinical significance and without clinical significance) status changes from baseline. Percentages

of abnormal readings without clinical significance and abnormal readings with clinical significance will also be summarized.

6.2.4. Vital Signs

Observed values and the change from baseline in vital sign parameters such as, supine position blood pressure, heart rate, respiratory rate, and tympanic temperature, will be listed and summarized descriptively by cohort/dose level and time point.

6.2.5. Electrocardiograms

Observed values and the change from baseline in ECG parameters will be listed and summarized descriptively by cohort/dose level and time point. Overall interpretation of 12-lead ECG profiles over time will be summarized by categorical levels of normal, abnormal not clinically significant, and abnormal clinically significant; shift tables will summarize the shifts from baseline to each post baseline visit.

6.2.6. Physical Examination

The clinical findings during physical examination will be listed.

6.2.7. 24 Hour Ambulatory Blood Pressure Monitoring

Mean day time (10:00 to 20:00) and night time (00:00-6:00) systolic and diastolic BP and heart rate will be summarized for each day from Day -2 to Day 5 and Day 77 to Day 82 (Fagard 2008).

Baseline for 24 hour ABPM will be derived using the mean of the pre-dose measurements from Day -1 to Day 1.

6.2.8. 24 Hour Holter ECG Monitoring

Observed values from 24-Hour Holter ECG will be summarized by time point for each assessment day. Parameters calculated over the entire day such as mean HR, mean difference between day and night HR, mean NN intervals, pNN50, RMS SD, SDANN and SDNN index will be summarized by day.

Heart Rate Variability will be assessed by the following parameters:

- Percentage Greater than 50 msec (PRR_GT50), aka pNN50, the percentage of successive differences in RR values greater than 50 milliseconds (can be increases or decreases) during the time period.
- RMS SD, the square root of the mean of the squares of successive differences between the RR values during the time period.
- Magid SD, also known as SDNN index, the average of five-minute period standard deviations of the RR intervals during the time period.
- Kleiger SD, also known as SDANN, standard deviation of all five-minute average RR intervals during the time period.

6.2.9. Immunogenicity

Anti-drug antibodies (ADAbs, anti-HM15136 antibodies) will be summarized categorically, displaying the tier 1 (putative positive and negative) and tier 2 (positive and negative) tests by cohort/dose level with positive tests further summarized by tier 3 absolute titer values and domain specificity.

Tier 3 neutralizing antibody (nAbs) results will be summarized with ADAbs data in the same table.

In a separate table, anti-polyethylene glycol antibodies (anti-PEG) will be summarized categorically, displaying the screening result and specificity. The Anti-PEG specificity test will only be performed for samples where the titer increased more than 4 times compared to Day 1.

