 - (1) Hematology
 - (2) Blood chemistry
 - (3) Blood coagulation
 - (4) Urine analysis
- (11) Pregnancy test (Urine)
- (12) Abbreviated PE
- (13) Concomitant medication
- (14) Adverse events
- (15) Drug abuse urine screening and alcohol exhalation test
- (16) Dietary education and counseling
- (17) Diet Diary Distribution

- (18) Body weight
- (19) BMI
- (20) Tympanic temperature
- (21) Waist circumference, Hip circumference, Waist-to-hip ratio (WHR)
- (22) Instructions on 7-point SMBG at home
- (23) SMBG Diary Distribution
- (24) Instructions on FBG measurements at home via glucometer

Per COVID-19 modification, Day -2 has a visit window of ± 1 day.

3) Day -1

- (1) Randomization
- (2) PD assessment
 - (1) MRI/MRI-PDFF
 - (2) FPG
- (3) 7-point Self-monitoring of blood glucose (SMBG)
- (4) ABP monitoring
- (5) Holter monitoring
- (6) Vital sign
- (7) Clinical laboratory test (not performed in Part 2)
 - (1) Hematology
 - (2) Blood chemistry
 - (3) Blood coagulation
 - (4) Urine analysis
- (8) Concomitant medication
- (9) Adverse events
- (10) Body weight

Per COVID-19 modification, Day -1 may be performed as a phone visit and only the following variables may be assessed/will be recorded:

- (1) PD assessment
 - (1) MRI/MRI-PDFF, only if available and MRI center can perform assessment
- (2) Reminder to perform and record 7-point self-monitoring of blood glucose (SMBG) and bring diary to next visit
- (3) Concomitant medication
- (4) Adverse events

Per COVID-19 modification, Day -1 has a visit window of ± 2 day.

4) Day 1

- (1) Administration IP
- (2) PK assessment
- (3) PD assessment
 - (1) Fructosamine, Glycated albumin
 - (2) FPG
 - (3) Fasting insulin, Fasting C-peptide
 - (4) HOMA-IR, HOMA- β
 - (5) Incretins / metabolic hormones
 - (6) Amino-acid profile

- (7) Serum lipid profiles
- (8) Inflammatory markers
- (9) β -hydroxybutyrate
- (4) 7-point SMBG
- (5) ABP monitoring
- (6) Holter monitoring
- (7) Vital signs
- (8) Clinical laboratory test
 - (1) Hematology
 - (2) Blood chemistry
 - (3) Blood coagulation
 - (4) Urine analysis
- (9) TSH
- (10) Amylase, lipase
- (11) Calcitonin
- (12) LH, FSH (Only female subject)
- (13) Injection site reactions
- (14) Immunogenicity (ADAbs, nAbs, anti-PEG)
- (15) Concomitant medication
- (16) Adverse events
- (17) Body weight
- (18) BMI
- (19) Waist circumference, Hip circumference, Waist-to-hip ratio (WHR)

Per COVID-19 modification, Day 1 may have additional assessments:

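### SAP 6.2.9 summarises ADA and nAb positivity without reference to the pre-dose result, so it reports prevalence and not treatment-emergent ADA

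*SAP*

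**What the plan says.** SAP 3.1.1 lists immunogenicity (ADA, neutralizing antibodies, anti-PEG) among the primary safety endpoints. SAP 6.2.9 gives the analysis:

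- ADA results are tabulated as categories, "displaying the tier 1 (putative positive and negative) and tier 2 (positive and negative) tests by cohort/dose level". A positive ADA result is then described by its absolute titer and by domain.
- For neutralizing antibodies: "Tier 3 neutralizing antibody (nAbs) results will be summarized with ADAbs data in the same table".
- Anti-PEG has its own table and "will be summarized categorically, displaying the screening result and specificity". Day 1 enters here only, as a condition for running a further assay: "The Anti-PEG specificity test will only be performed for samples where the titer increased more than 4 times compared to Day 1".

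Protocol 11.2.7, item 9, adds a by-subject listing and a summary by cohort/dose level with placebo combined. It has no baseline rule.

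The samples exist. The Day 1 list in Protocol 10.2.1 includes "Immunogenicity (ADAbs, nAbs, anti-PEG", and the same item appears on Days 15, 29, 57, 78, 85 and 113. SAP 6.1.2 defines baseline generally as the last non-missing value before the first dose, but 6.2.9 does not apply it to ADA.

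**The concern.** The endpoint is meant to show what 12 weeks of dosing does. For ADA, that is the number of subjects who develop antibodies after dosing, or whose existing antibodies rise. A count of positives by dose level answers a different question, because it mixes reactivity that was there before dosing with reactivity that arose during it.

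The groups are small enough for this to matter. Most dose groups have nine active subjects, so a single subject with pre-existing reactivity can create or hide an apparent dose pattern. No eligibility criterion in Protocol 5.3 excludes such subjects. Protocol 3.4 reports anti-HM15136 antibody in monkeys, so an induced response is a realistic possibility and needs to be separable from background.

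Elsewhere the SAP does make this separation. Section 6.2.1 counts a pre-existing adverse event as treatment-emergent only if it worsens in severity or frequency. Sections 6.2.3 and 6.2.5 use shift tables from baseline for laboratory and ECG results.

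**Working it through.** The documents state no figure on this point, so there is nothing to reproduce. The check has three parts.

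**1. Does any permitted layout of the table separate the two kinds of subject?** Section 6.2.9 does not say whether it counts tests or subjects, whether it is split by visit, or whether Day 1 is included. Take an assumed group of nine active subjects: one is positive at a stable titer from Day 1, one seroconverts after dosing, and seven are always negative.

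- *Subjects ever positive, with or without Day 1:* 2/9 = 22.2%. Treatment-emergent ADA is 1/9 = 11.1%, or 1/8 = 12.5% of those negative at baseline.
- *Tests pooled over visits:* seven time points give 9 × 7 = 63 scheduled tests. The stable positive supplies 7/63 = 11.1%. With Day 1 left out, the figure is 6/54 = 11.1%. Neither contains any induced antibody.
- *By visit, with a Day 1 column:* 1/9 on Day 1 and 2/9 at visits after seroconversion. The reader sees the background and can subtract. The difference is a net change, though, and equals the number of seroconverters only if nobody moves from positive to negative. The table does not link a subject's results across visits.

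No layout identifies a boosted response, since 6.2.9 summarises absolute titers of positive tests and not the ratio to the pre-dose titer.

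**2. Size per subject.** Planned active subjects (SAP Table 1): nine in Cohorts 1–3 and 5–7, fifteen in Cohort 4.

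- 1/9 = 11.1 percentage points
- 1/15 = 6.7 percentage points

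**3. How likely is at least one such subject?** The documents give no prevalence *p* of pre-dose ADA positivity, so *p* is an assumption. The chance is 1 − (1 − p)^n. For example, with p = 5% and n = 9: 1 − 0.95^9 = 1 − 0.630 = 0.370.

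| Assumed p | n = 9 | n = 15 |
|---|---|---|
| 1% | 8.6% | 14.0% |
| 2% | 16.6% | 26.1% |
| 5% | 37.0% | 53.7% |
| 10% | 61.3% | 79.4% |

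**The case against.** The strongest reply is that the information will be available. Results are listed by subject, titers of positives are shown, and placebo is pooled within each part (9 planned in Part 1, up to 15 + 9 = 24 in Part 2), which indicates background reactivity. With nine active subjects and seven samples each, a reader can trace every case. The analysis is descriptive, the sample size is not powered, and no stopping criterion in Protocol 7.3 names ADA. A treatment-emergent flag could be derived later.

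This limits the harm and is why the point is a repair and not a flaw in the design. It does not remove the gap. Pooled placebo cannot reclassify a particular subject in a particular dose group. Reconstruction from listings would set the fold-rise for a boosted response after the data are known, for a primary endpoint.

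Two stronger readings are tempting, and the documents do not support them:

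- A reader might infer that the SAP attributes pre-dose antibodies to HM15136. It does not say so. Section 6.2.9 is silent on visit split, on Day 1 and on the counting unit. What follows from the text is that the summary does not distinguish the two kinds of positive.
- A reader might infer that the SAP adjusts anti-PEG for Day 1 while leaving ADA unadjusted. The restriction to "samples where the titer increased more than 4 times compared to Day 1" only selects samples for the specificity test. The anti-PEG screening result is displayed without a Day 1 reference, just as ADA is. For the same reason that factor should not be carried over as the criterion for boosted ADA: it is an assay trigger for another antibody, and the documents give no assay information to support it here.

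**Conclusion.** The point holds as an omission. For a primary safety endpoint with a scheduled Day 1 sample, neither document compares ADA or nAb status with the pre-dose result or defines a treatment-emergent response. One stable pre-dose positive shifts the subject-level rate by 11.1 points in a 9-subject group, or by 6.7 points in Cohort 4. Those sizes assume counting by subject and full planned enrolment; Cohort 4 may close with fewer than 15, which would make the shift larger. The likelihood of such a subject rests wholly on an assumed prevalence and cannot be narrowed from the documents.

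One detail must be settled for any repair to work. Neither the Day 1 list in Protocol 10.2.1 nor item 14 of Protocol 10.2.2 says that the Day 1 immunogenicity sample is drawn before dosing.

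**What to change.** Add to SAP 6.2.9 a by-subject summary for each dose level and for pooled placebo. Use the SAP 6.1.2 baseline, with a statement that the Day 1 immunogenicity sample is pre-dose. Show:

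- (a) baseline-positive prevalence;
- (b) treatment-induced ADA: negative at baseline and confirmed positive after dosing;
- (c) treatment-boosted ADA: positive at baseline with a titer rise of at least a prespecified fold suited to the ADA assay.

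The denominator should be subjects with a baseline result and at least one post-dose result. Show nAb status within these groups.

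Fix the rule before Part 2 is unblinded. The SAP introduction places the current amendment after the Part 1 database lock, so any use in Part 1 should be labelled as added after lock.

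The cost is a derived flag and a few table rows from data already collected. The reported incidence may be lower than the unconditioned count.
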